1. SYNOPSIS

Sponsor / Sponsor-Investigator	Ivoclar Vivadent AG
Title:	Retrospective clinical evaluation of nano-hybrid-composite denture teeth SR Phonares II
Short title / Investigation ID:	Retrospective clinical evaluation of SR Phonares II Investigation ID: LL 5267725
Clinical Investigation Plan, version and date:	Version 2.0, 19.09.2022
Registration:	Registry at ClinicalTrials.gov of the U.S. National Library of Medicine (http://www.clinicaltrials.gov): The trial additionally registers in the supplementary federal database (Portal for clinical trials in Switzerland - SNCTP, https://www.kofam.ch/en/snctp-portal/) with its submission on BASEC. Furthermore, as soon as the new electronic system EUDAMED2 is operational, the clinical investigation will be retrospectively registered, if required.
Category and its rationale:	Category A1 The medical device has conformity marking and will be used according to its instruction for use. The subjects are not subjected to any additional invasive or stressful procedures compared with those applied under normal conditions of use of the product.

Name of the MD, Unique Device Identification (UDI), name of the manufacturer	SR Phonares II Article UDI SR Phonares II Ant. 6er OS71 A2 DIVO6448651 SR Phonares II Ant. 6er OS71 A3 DIVO6448661 SR Phonares II Ant. 6er OS72 A3 DIVO6448861 SR Phonares II Ant. 6er OB71 A3 DIVO6450461 SR Phonares II Ant. 6er OB72 A3 DIVO6450661 SR Phonares II Ant. 6er OB73 A3 DIVO6450861 SR Phonares II Ant. 6er OB73 A3.5 DIVO6450871 SR Phonares II Ant. 6er UL50 A2 DIVO6451651 SR Phonares II Ant. 6er UL51 A3 DIVO6451861 SR Phonares II Ant. 6er UL51 A3.5 DIVO6451871 SR Phonares II Ant. 6er UL52 A3 DIVO6452061 SR Phonares II Ant. 6er UL53 A3 DIVO6452261 SR Phonares II Typ 8er ONU3 A3 DIVO6453661 SR Phonares II Typ 8er ONU5 A3 DIVO6453861 SR Phonares II Typ 8er ONU5 A3.5 DIVO6453871 SR Phonares II Typ 8er ONU6 A3 DIVO6454061 SR Phonares II Typ 8er UNL3 A2 DIVO6454251 SR Phonares II Typ 8er UNL5 A3 DIVO6454461 SR Phonares II Typ 8er UNL5 A3.5 DIVO6454471 Ivoclar Vivadent AG [name]
Stage of development:	Post-market stage with CE marking
Background and rationale:	This retrospective study investigates the longevity of dentures with SR Phonares II teeth after a wearing period of more than 10 years.
Objective(s):	The primary objective is to assess the survival rate of dentures with SR Phonares II teeth after more than 10 years. The secondary objectives asses the quality of the dentures concerning aesthetic, functional and biological properties.
Outcome(s):	The primary outcome of the study is the survival rate of the dentures with the tested denture teeth. The secondary outcomes are all linked to the quality of the materials used (surface lustre, staining, plaque accumulation, color match, aesthetic anatomical form, fracture, marginal adaptation, occlusal contour, wear patients view, integrity of adjacent natural teeth, adjacent mucosa, oral health).
Design:	Retrospective evaluation

Inclusion / exclusion criteria:	Subjects fulfilling all inclusion criteria are eligible for the investigation: informed consent signed and understood by the subject, partial or full denture with SR Phonares II teeth, dentures delivered in the internal clinic between August 2010 and August 2012, to be able to visit the internal clinic (Exception: Patients with limited mobility are also included if another person can carry the dentures to the internal clinic of Ivoclar Vivadent AG for the examination.). The presence of any of the following exclusion criteria will lead to the exclusion of the subject: patient does not wear the dentures regularly, health status (physical and mental) does not allow participation.
Measurements and procedures:	The intraoral situation will be examined similar to a standard dental examination. The dentures are then removed, cleaned and examined extraoral. Pictures and an impression of the dentures are taken.
Intervention:	The examinations do not differ from standard dental examinations. Impressions of the back teeth of the dentures are taken extraoral and stone casts are poured. They are used for analysis of wear and microscopical analysis.
Control intervention (if applicable):	n.a.
Number of subjects with rationale:	22 patients that were supplied with dentures with SR Phonares II teeth (in total 43 dentures) in the internal clinic of Ivoclar Vivadent AG between August 2010 and August 2012.
Duration of the investigation:	6 months
Investigation schedule:	October 2022 First- subject –In (planned) March 2023 Last- subject –Out (planned)
Investigator(s):	[name] [name] Fürstentum Liechtenstein Tel.: [REDACTED] Mail: [REDACTED]
Investigational Site(s):	This is a single centre study. R&D Clinic Ivoclar Vivadent AG [name] Fürstentum Liechtenstein
Statistical considerations:	Since the study is retrospective with a small cohort and no control group, mainly descriptive statistical analysis will be performed. The obtained data, especially the survival rate will be discussed and compared with data from the literature. A minimal sample size of 41 dentures was calculated with absolute error (precision of 10% and standard normal variate of 5% (type 1 error)).
Compliance statement:	This investigation will be conducted in compliance with the CIP, the current version of the Declaration of Helsinki, ISO14155, ICH-GCP (as far as applicable) as well as all national legal and regulatory requirements.

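### The regular-wear exclusion can remove patients whose dentures failed before denture survival, the primary outcome, is counted; this biases the survival rate upward by an unknown amount

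*Combined protocol and SAP*

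**What the plan says.** All references are to the combined protocol and SAP.

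- **Objective (section 1, Synopsis).** "The primary objective is to assess the survival rate of dentures with SR Phonares II teeth after more than 10 years". The primary outcome is the survival rate of the dentures. The background row describes longevity "after a wearing period of more than 10 years".
- **Cohort (section 1, number of subjects).** "22 patients that were supplied with dentures with SR Phonares II teeth (in total 43 dentures").
- **Eligibility (section 1, inclusion / exclusion criteria).** Subjects need signed consent, a partial or full denture with the study teeth, and "dentures delivered in the internal clinic between August 2010 and August 2012". They also have "to be able to visit the internal clinic", with an exception for limited mobility when someone else can bring the dentures. A subject is excluded if the "patient does not wear the dentures regularly", or if health does not allow participation.
- **Timing (sections 1 and 4).** Primary variables are recorded at one recall, planned between October 2022 and March 2023. Device deficiencies are recorded at the same visit.
- **Analysis (section 1, statistical considerations).** The analysis is mainly descriptive, there is no control group, and the survival rate is to be compared with the literature. The minimum sample is 41 dentures, for 10% absolute precision and a 5% type 1 error.

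The supplied text does not say what counts as failure. Nor does it say how a denture that is no longer worn, discarded or replaced enters the numerator or denominator.

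**The concern.** Eligibility is tied to the outcome. Regular wear more than ten years after delivery is partly a consequence of the denture having survived. People stop wearing a denture for several reasons, but failure and replacement are among the obvious ones. Applied as written, the rule can remove such a patient from the study before the primary outcome is recorded. The result would then describe dentures still in use rather than dentures delivered.

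The exclusion is reasonable for the secondary outcomes, such as wear, staining and surface lustre, which need a denture in regular use. It does not suit a survival rate.

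At stake is the study's only benchmark. Without a control group, the survival rate is interpreted by setting it against published figures, and a denominator that has lost failures makes that comparison look better than it should.

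**Working it through.** **Inputs from the documents.** 43 dentures, 22 patients, minimum 41 dentures, precision 10%, type 1 error 5%, deliveries August 2010 to August 2012, recall October 2022 to March 2023.

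**Inputs assumed.** Six failures by recall, a 10-year survival of 88%, and a constant hazard. None of these is in the documents.

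**The plan's own figure.** For a single proportion, n = z² p(1 − p)/d². With z = 1.96 and d = 0.10, p = 0.88 gives 3.8416 × 0.1056/0.01 = 40.57, rounded up to 41. The synopsis does not state the expected proportion: p = 0.80 would give 62 and p = 0.90 would give 35. So 41 is consistent with about 88% but cannot be confirmed.

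**Effect of the exclusion.** The criterion acts on subjects, so all of a patient's dentures leave together. With 43 dentures in 22 patients, most patients have two. Six failures among 43 leave 37 surviving.

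| Excluded for irregular wear | Observed rate | Difference from 37/43 (points) |
|---|---|---|
| Nobody | 37/43 = 86.0% | 0 |
| One patient, one failed and one surviving denture | 36/41 = 87.8% | +1.8 |
| Two such patients | 35/39 = 89.7% | +3.7 (below the minimum of 41) |
| One patient, both dentures failed | 37/41 = 90.2% | +4.2 |

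Removing a patient raises the rate whenever the failed share of that patient's dentures exceeds the failed share overall. Here 1/2 = 50% exceeds 6/43 = 14.0%, so one failure in a pair is enough. Two of the three exclusion scenarios leave exactly 41 dentures, so reaching the planned minimum gives no protection.

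The converse also holds. Excluding a non-wearer whose two dentures are both counted as surviving gives 35/41 = 85.4%, or 0.7 points lower. The upward bias therefore comes from exclusions linked to failure.

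**Denture age at recall.** Shortest: 31 August 2012 to 1 October 2022 is 3683 days, and 3683/365.25 = 10.08 years. Longest: 1 August 2010 to 31 March 2023 is 4625 days, and 4625/365.25 = 12.66 years. With dates spread uniformly the mean age is 11.37 years. At 88% 10-year survival and a constant hazard, survival at recall is about 0.88^(11.37/10) = 0.865, which is 1.5 points below the 10-year figure.

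**Precision for scale.** At 88%, the 95% half-width is 1.96 × √(0.88 × 0.12/43) = 9.7 points if dentures are independent. It is 1.96 × √(0.88 × 0.12/22) = 13.6 points if dentures within a patient are fully correlated.

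**The case against.** The strongest reply is that the supplied text holds only a synopsis, abbreviations, an empty revision table and a schedule. A failure definition, an estimator and rules for missing dentures may stand in later chapters. This is right for everything that is merely unstated, and the point is limited accordingly. It does not answer the regular-wear exclusion, which is a stated rule.

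A second reply is that failures may still be captured. Device deficiencies are recorded at recall, and a mobile patient with a failed denture can still attend. The attendance criterion by itself therefore does not show that failed dentures drop out, and it is not relied on here. But recording deficiencies at recall does not help with a patient excluded for irregular wear, and nothing in the supplied text says that such a patient's dentures are counted.

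A third reply is that the size is speculative. This stands. The effect depends on how many patients are excluded and on how failures cluster within patients. The 90.2% reading needs both failures in one patient.

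A reader might go further and infer that the reported rate is not survival at any defined time. The documents do not support so flat a conclusion. Every denture is past ten years at recall, which fits the stated objective. The age spread costs only about 1.5 points under the assumptions shown, and silence in an excerpt does not show that no time point or estimator exists. Nor do the documents show that failures are in fact dropped, only that the rule permits it.

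**Conclusion.** The concern holds in this form: a stated eligibility rule can remove failed dentures from the primary outcome, and nothing in the supplied text corrects for it. Where exclusions are linked to failure the bias is upward. With six assumed failures it is 1.8 to 4.2 points for one excluded patient. That is smaller than the 9.7 to 13.6-point half-width, but it is systematic and falls on the number meant for comparison with the literature. The true size is unknown.

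The spread of denture ages, 10.08 to 12.66 years, is a secondary matter of comparability. It rests on planned dates and on the outer edges of the calendar months. The missing failure definition is a gap in the supplied text only.

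**What to change.** 1. Apply the regular-wear exclusion only to the examined secondary outcomes, and keep all 43 delivered dentures in the denominator of the primary outcome. If that is not possible, report a sensitivity analysis that counts as failures the dentures of consenting subjects that are no longer worn, discarded or replaced.
2. State before recall what counts as failure, including how dentures that are replaced, discarded or no longer worn are classified.
3. Report how many of the 22 patients were not recalled or were excluded, with reasons.
4. Report denture ages with the rate. Where delivery and failure dates can be retrieved, also give survival at 10.0 years for comparison with literature figures. Every denture can reach that age before recall. If there are no earlier losses, this is the simple proportion surviving to year 10.
5. Give a patient-clustered 95% confidence interval, since 43 dentures come from 22 patients.

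**Cost.** A few sentences in the analysis plan, up to two dates for each of at most 43 dentures, and a count of patients. Restricting the exclusion needs an eligibility amendment. Some failure dates will be approximate, which affects the 10-year figure only where the uncertain interval spans 10.0 years. Because signed consent is required, data on patients who do not consent may be unavailable. In that case the full denominator cannot be completed and the counts in item 3 carry more weight. The resulting rate may also be less favourable.

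### Cheap improvement: the device is the denture tooth, but survival is counted per denture with no cause of failure attached, and the exclusion of irregular wearers can remove failed dentures from the count

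*Combined protocol and SAP*

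**What the plan says.** All references are to the combined protocol and SAP.

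- **Device** (section 1, Title and UDI list): the title is "Retrospective clinical evaluation of nano-hybrid-composite denture teeth SR Phonares II", and every listed article is a set of teeth.
- **Objective** (section 1, Objective(s)): "The primary objective is to assess the survival rate of dentures with SR Phonares II teeth after more than 10 years".
- **Outcomes** (section 1, Outcome(s)): "The primary outcome of the study is the survival rate of the dentures with the tested denture teeth". Fracture, wear, staining and other quality items are secondary.
- **Procedures** (section 1, Measurements and procedures): after the intraoral examination, "The dentures are then removed, cleaned and examined extraoral".
- **Schedule** (section 4): there is one recall visit, at which primary variables, secondary variables, adverse events and device deficiencies are all recorded.
- **Exclusion** (section 1, Inclusion / exclusion criteria): a subject is excluded if the "patient does not wear the dentures regularly".
- **Cohort** (section 1, Number of subjects): 22 patients with 43 dentures.
- **Analysis** (section 1, Statistical considerations): mainly descriptive, with no control group. "The obtained data, especially the survival rate will be discussed and compared with data from the literature".

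The text available ends at section 4. It does not define a failed denture, list causes of failure, or say how a replaced study tooth counts.

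**The concern.** A denture can be lost for reasons that have nothing to do with its teeth. A denture can also remain in service after one of its study teeth was replaced. A single all-cause denture survival figure does not separate these cases, and there is no comparator to help. A reader who takes the rate as evidence about the teeth may credit or blame them wrongly.

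The planned tooth-level assessments do not close the gap. Fracture and wear are judged on dentures examined at the recall, and a denture already discarded cannot be examined. Device deficiencies are also recorded at the recall, but nothing links them to survival.

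The exclusion adds a second problem. A denture that failed may for that reason no longer be worn. If its owner is then excluded, the failure leaves the denominator, and the survival rate rises for a reason unrelated to durability.

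**Working it through.** **1. The plan's own figure.** The stated minimum is 41 dentures, from an absolute precision of 10% and a type 1 error of 5%. The expected survival p is not stated. The usual formula is n = z²p(1−p)/d², with d = 0.10 and z = 1.96.

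- p = 0.88 gives 3.8415 × 0.88 × 0.12 / 0.01 = 40.57, rounded up to 41.
- p = 0.90 gives 35, p = 0.85 gives 49 and p = 0.50 gives 97.
- Solving back from n = 41: p(1−p) = 41 × 0.01 / 3.8415 = 0.1067, so p = 0.8785 (or its complement, about 0.12). If n was just above 40 and rounded up, p = 0.882.

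The 41 can therefore be reached with p of about 0.88, but this is inferred. It is used below only to choose an illustrative number of failures.

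**2. Illustrative failures among 43 dentures (assumption, with range).**

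| Assumed survival | Basis | Failures in 43 | Possible tooth-related losses |
|---|---|---|---|
| 0.95 | alternative value | 43 × 0.05 = 2.15, about 2 | 0 to 2/43 = 4.7% |
| 0.88 | back-solved, z = 1.96 | 43 × 0.12 = 5.16, about 5 | 0 to 5/43 = 11.6% |
| 0.81 | back-solved, one-sided z = 1.645 | 43 × 0.19 = 8.17, about 8 | 0 to 8/43 = 18.6% |

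With 5 failures, denture survival is 38/43 = 88.4% (exact 95% interval 74.9% to 96.1%, ignoring clustering within patients). That result is the same for every split by cause. Each denture classed differently moves a proportion by 1/43 = 2.3 points.

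**3. Effect of the exclusion, with 5 failures.** The exclusion removes subjects, not single dentures. The cohort averages 43/22 = 1.95 dentures per patient, so removing a patient usually removes about two.

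| Failures removed | Where they sit | Remaining survival |
|---|---|---|
| none | – | 38/43 = 88.4% |
| two | both in one two-denture patient | 38/41 = 92.7% |
| two | in two different two-denture patients, each with one surviving denture | (38−2)/(43−4) = 36/39 = 92.3% |
| all five | any arrangement | 100% |

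In these cases removing two failures adds about 4 points, and removing all five adds 11.6 points.

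**The case against.** The strongest reply is that this argues from silence. A synopsis need not carry failure definitions or cause codes, and the schedule refers to primary and secondary variables without itemising them. That stands, and it makes the point conditional on the sections not available.

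A second reply is that denture longevity is what the background, objective and primary outcome consistently address. That also stands. A reader might infer that the primary outcome is wrong or contradicts the objective; the documents do not support this.

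Third, tooth-level information is planned: fracture and wear are outcomes, device deficiencies are scheduled, and a retrospective design does not rule out past records. A reader might infer that the plan ignores the teeth, and that would be wrong. What is missing is the link from this information to survival, particularly for dentures no longer in use.

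Fourth, it is tempting to say that a replaced study tooth leaves the survival rate untouched. The text does not define survival, so such a replacement could count as failure. The uncertainty is a reason to record these events, but the stronger statement is unsupported.

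Finally, the magnitudes rest on an assumed number of failures. That is correct, and nothing in the argument depends on 0.88 being the planners' value.

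**Conclusion.** The point holds as an inexpensive improvement, limited to the text available. The survival rate to be set against the literature is per denture and carries no cause of failure, so it cannot alone be read as performance of the teeth. The exclusion of irregular wearers can remove failed dentures and push survival upward.

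The size is illustrative. It assumes 5 failures in 43 and two-denture patients where stated. Tooth-related losses could then lie anywhere from 0% to 11.6% behind the same 88.4%, and the exclusion could lift that figure to 92.3% or 92.7% (two failures removed) or to 100% (all removed). How many failures occurred, what caused them, and whether the exclusion removes any are unknown. A reader might infer that the estimate is biased by a known amount; the documents show only that the rule permits bias in that direction.

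**What to change.** 1. Keep denture survival as the primary outcome. Where consent and records allow, count a denture no longer worn because it failed or was replaced as a failure among the 43 delivered, instead of losing it through the exclusion. Report how many of the 43 have no information.
2. From clinic records, patient history and device-deficiency entries, record for each denture whether a tooth-related event ever occurred, including replacement of a study tooth: yes, no or unknown.
3. Report one descriptive cross-table that sums to 43: denture status (in service, lost, no information) by tooth-related event (yes, no, unknown), with the main cause of each loss listed. A tooth replaced in a denture later lost for another reason is then still counted, and unknown causes do not blur lost and in-service dentures.
4. Read both figures from that table, with unknowns counted both ways. With a in service and m without information, survival lies between a/43 and (a + m)/43. With Y tooth-related events and U unknown, the proportion with any tooth-related failure lies between Y/43 and (Y + U)/43. Both are descriptive; dentures are clustered within 22 patients, so intervals that ignore this may be too narrow.

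**Cost.** A few case report form entries, a record look-up for up to 43 dentures, and one table. The sample size does not change. Some causes will be unknown after 10 years, because the text does not show that clinic records hold them, and the survival figure may be less favourable. If later sections already provide this, nothing needs to change.

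### Excluding patients who do not wear their dentures regularly, apparently judged at recall, can remove failed dentures from the primary survival rate

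*Combined protocol and SAP*

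**What the plan says.** All of this is in the Synopsis (section 1) and the Investigation schedule (section 4).

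- Outcome: "The primary outcome of the study is the survival rate of the dentures with the tested denture teeth". The objective sets the horizon at more than 10 years.
- Eligibility: "dentures delivered in the internal clinic between August 2010 and August 2012", plus "informed consent signed and understood by the subject" and a visit to the clinic. Patients with limited mobility are accepted "if another person can carry the dentures to the internal clinic".
- Exclusion: "criteria will lead to the exclusion of the subject: patient does not wear the dentures regularly". No date for this judgement is given. The other exclusion is health status.
- Number of subjects: "22 patients that were supplied with dentures with SR Phonares II teeth (in total 43 dentures").
- Examination: after the intraoral check, "The dentures are then removed, cleaned and examined extraoral".
- Timing: "October 2022 First- subject" in, with the last subject out planned for March 2023. The schedule has a telephone contact at day -3, then consent and recall on day 0. The primary variables are entered only at the recall. There is no row for eligibility or records review.
- Statistics: mainly descriptive, no control group, the survival rate to be set against the literature, and a minimum of 41 dentures for a precision of 10%.

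**The concern.** Survival is a property of a denture from its delivery onward. Regular wear, judged a decade later, is partly a consequence of whether the denture survived. A denture that broke beyond use, was replaced or was abandoned because it failed would normally not be in regular wear. If its owner is excluded for that reason, the failure leaves both numerator and denominator, and what remains is closer to survival among current wearers than survival among the dentures supplied.

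The criterion suits the secondary outcomes, since lustre, staining and wear can only be rated on a denture in use. For the primary outcome it selects on the result. No control arm is present in which the same selection might cancel, and a published comparison rate may rest on a different denominator. A reader of the report could not tell the two kinds of rate apart.

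**Working it through.** **Inputs.** From the Synopsis: 22 patients, 43 dentures, delivery August 2010 to August 2012, recall October 2022 to March 2023, minimum 41 dentures, precision 10 points, type 1 error 5%. Not in the document, and therefore assumed below: the expected survival, the number of failures, the number of dentures per patient, and that the 43 are all the dentures delivered in the window.

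**1. When wear is judged.** Shortest interval: August 2012 to October 2022 = 10 years 2 months. Longest: August 2010 to March 2023 = 12 years 7 months (12.6 years). Both contacts in the schedule, day -3 and day 0, fall after the follow-up being assessed, so it does not matter which of them is used.

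**2. The plan's 41.** With n = z²p(1−p)/d² and d = 0.10, the figure cannot be reproduced from the stated inputs alone, because neither p nor sidedness is given. With z = 1.96 and p = 0.88, n = 3.8416 × 0.1056/0.01 = 40.6, rounded up to 41; p from 0.8785 to 0.8819 gives 41. One-sided, p of about 0.814 to 0.819 is needed. On 43 dentures these imply 5.1 to 5.2 failures, or about 8. They serve only to choose illustrations.

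**3. Bias in general.** Let F of 43 dentures have failed, and let e be left out, k of them failed. Then

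observed − true = (43−F−(e−k))/(43−e) − (43−F)/43 = (43k − Fe)/(43(43−e)).

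This is positive only if k/e > F/43, that is, if the failed share among excluded dentures exceeds the overall failed share.

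**4. Cap if 41 are evaluated.** Then e ≤ 2. The largest value is at e = k = F = 2: 41/41 − 41/43 = 2/43 = 4.7 points, under half the planned precision.

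**5. Illustrations with F = 5** (true rate 38/43 = 88.4%):

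| Dentures left out (e) | Failed among them (k) | Observed | Bias (points) |
|---|---|---|---|
| 2 | 0 | 36/41 = 87.8% | −0.6 |
| 2 | 1 | 37/41 = 90.2% | +1.9 |
| 2 | 2 | 38/41 = 92.7% | +4.3 |
| 4 | 0 | 34/39 = 87.2% | −1.2 |
| 4 | 1 | 35/39 = 89.7% | +1.4 |
| 4 | 2 | 36/39 = 92.3% | +3.9 |
| 6 | 3 | 35/37 = 94.6% | +6.2 |
| 5 | 5 | 38/38 = 100% | +11.6 |

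The sign changes at a failed share of 5/43 = 11.6%. The rows with one failed and one intact denture per patient presuppose that such a patient is excluded, which the rule does not clearly require. At the extreme where every failure is left out, the bias is F/43: 4.7 points for F = 2, 9.3 for 4, 11.6 for 5 and 18.6 for 8.

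**6. How easily 41 is missed.** If no patient has more than two dentures, 2a + (22−a) = 43 gives a = 21 patients with two and one with one. Losing one patient leaves 41 or 42 dentures; losing two, for any reason, leaves 39 or 40.

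**The case against.** The case on the other side has real force in several places.

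- **Size.** If the planned minimum is met, the bias is capped at 4.7 points; anything larger needs a shortfall from 41. The row-by-row sizes also rest on an assumed failure count. No test or decision rule in the available text depends on the rate. This stands, and it limits the severity.
- **A rule per patient.** A patient who lost one denture and wears the other may stay enrolled, with the failure recorded. Damaged dentures still worn remain eligible, and fracture is itself a rated outcome. This also stands. A reader might infer that every failed denture is excluded and the rate is driven towards 100% by construction; the wording does not support that.
- **Direction.** A reader might infer that the rate must be inflated. Some non-wear has nothing to do with the teeth, and excluding a patient can remove intact dentures, so the bias may be nil or slightly downward.
- **Missing chapters.** The available text stops at section 4. A definition of failure or a reconciliation to 43 may appear later, so their absence cannot be counted as a fault. Even so, a definition of failure would not by itself count a denture whose owner is excluded.
- **Data source.** The schedule shows when the primary variables are entered, not where they come from, and the same clinic delivered the dentures. Records could inform the entry, but for enrolled subjects only.
- **The denominator.** The document does not say that the 43 are every denture delivered in the window; they may already be the reachable patients. Every percentage above depends on this.
- **Intended target.** The Background speaks of a wearing period, so survival under regular use may be what is meant. That is a legitimate target, but the objective does not state it.

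**Conclusion.** The concern holds in a limited form: a stated eligibility rule makes entry into the primary estimate depend on a state that denture failure can bring about. The documents fix neither the size nor the sign of the resulting bias. It is upward if excluded dentures failed more often than retained ones, and at most 4.7 points if at least 41 of the 43 listed dentures are evaluated. It can be larger only with fewer than 41, and nothing in the available text enforces that number.

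The conclusion rests on reading the schedule as placing the wear judgement at the call or recall, and on the 43 being the full set delivered, which is an assumption. It should be fixed, because it affects what the only primary outcome means. The evidence does not support calling the survival rate invalid.

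**What to change.** 1. Apply the regular-wear criterion only to the secondary quality ratings.
2. For the primary outcome, record the status of each of the 43 listed dentures, from clinic records or the patient and within the consent or ethics cover available: in service, failed for a device-related reason (the sponsor to define), out of use for an unrelated reason, or unknown. Count device-related non-use as failure.
3. Report in service/(in service + failed), always beside best-case and worst-case bounds over all 43. The known-status rate alone still drops unknowns, so it is not a sufficient remedy. For example, 33 in service, 5 failed, 2 unrelated and 3 unknown gives 33/38 = 86.8%, with bounds 33/43 = 76.7% and 38/43 = 88.4%. If only 33 dentures are known and all are in service, the rate is 100% but the bounds are 76.7% to 100%. The bounds also cover selection through consent, attendance and health status.
4. Give the number excluded, with reasons, and state whether the 43 are all dentures delivered in the window.
5. If survival among regular wearers is the intended target, say so in the objective, label the rate that way, and still report the status of all 43.

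The cost is a change of wording plus record retrieval reaching back up to about 12.6 years; the available text does not show how much can be recovered. The telephone contact precedes consent, so individual status for people who do not consent needs ethics cover; without it they enter only the bounds, as counts. The bounds may be wide, and the reported rate may be less favourable.

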4. INVESTIGATION SCHEDULE

Investigation Periods	Patient information	Consent (ICF)	Recall
Visit	0	1	1
Time (day)	-3	0	0
Patient Information by phone	x		
Patient consent (ICF)		x	
Primary Variables			x
Secondary Variables			x
Dental radiograph			(x)
Adverse events			x
Device Deficiencies			x

(x) dental radiographs of a single tooth or dental implant will only be taken if necessary for medical reasons independent of the clinical trial.

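### Does cleaning before the extraoral examination spoil the plaque outcome for dentures brought in without the patient?

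*Combined protocol and SAP*

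**What the plan says.** All of this comes from section 1 (Synopsis), apart from the timing of the visit.

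- **Outcome(s).** The secondary list includes "surface lustre, staining, plaque accumulation, color match, aesthetic anatomical form". It also includes items that can only be judged in the mouth: "integrity of adjacent natural teeth, adjacent mucosa, oral health".
- **Measurements and procedures.** The first step is intraoral: "The intraoral situation will be examined similar to a standard dental examination". The next is: "The dentures are then removed, cleaned and examined extraoral".
- **Inclusion / exclusion criteria.** Attendance is required, with one exception: "Patients with limited mobility are also included if another person can carry the dentures to the internal clinic".
- **Number of subjects with rationale.** The cohort is "22 patients that were supplied with dentures with SR Phonares II teeth (in total 43 dentures".
- **Section 4 (Investigation schedule).** The row "Secondary Variables" is marked once, at the recall visit. The table gives no order of steps within that visit.

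The text does not say at which step plaque is scored or on what scale. It gives no separate procedure for dentures that arrive without their wearer.

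**The concern.** Cleaning removes what a plaque score is meant to measure. A patient who attends is examined intraorally before cleaning, so plaque can be seen in time. A carried-in denture has no such step. Read literally, the described order would give it one examination, after cleaning, and the denture would tend to be recorded as plaque-free whatever its state on arrival.

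The error would run one way, towards under-recording, and with a single recall visit the score could not be repeated. The sponsor wrote the exception into the inclusion criteria, so such dentures are foreseen. At stake is the plaque summary of a product evaluation, which would look somewhat better than it should.

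**Working it through.** **Reading the text.** For the described order to bias the plaque summary, four things must all happen:

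1. At least one denture arrives without the patient. The documents give no count.
2. It is cleaned before anyone looks at it. The described sequence starts with an intraoral examination and goes on to removal, which presupposes a patient in the chair. Nothing extends it to carried-in dentures.
3. Plaque is scored on it anyway, rather than on receipt or left missing. The plan does not tie plaque to the extraoral step.
4. The cleaned denture shows no residual plaque.

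None of the four is stated. If 1, 2 or 3 fails, there is no under-recording.

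**The plan's own figure.** The only computed figure is in Statistical considerations: "A minimal sample size of 41 dentures was calculated with absolute error (precision of 10" per cent and a 5% type 1 error. With n = z²p(1−p)/d², z = 1.96 and d = 0.10, an assumed proportion p = 0.88 gives 40.57, rounded up to 41. The plan does not state p, so 41 cannot be reproduced from its stated inputs alone. The figure does not concern plaque; 41 and the 10 points serve below only as a denominator and a yardstick.

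**Upper limit of the effect.** From the documents: 43 dentures, 22 patients, minimum 41. Assumed: two dentures per carried-in patient (43/22 = 1.95); plaque scored present or absent; all dentures pooled; the same true prevalence p in both groups; attended dentures scored correctly; every cleaned carried-in denture scored plaque-free. With k carried-in dentures among N examined, the drop in recorded prevalence is p·k/N. At p = 50%, in percentage points:

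| Carried-in patients (dentures k) | N = 43 | N = 41 | N = 30 (assumed) |
|---|---|---|---|
| 0 (0) | 0 | 0 | 0 |
| 1 (2) | 2.3 | 2.4 | 3.3 |
| 2 (4) | 4.7 | 4.9 | 6.7 |
| 4 (8) | 9.3 | 9.8 | 13.3 |

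For example, 0.50 × 4/43 = 4.7 points. At N = 43 and k = 8 the drop is 3.7 points if p = 20% and 14.9 if p = 80%. If cleaning hides only half of the plaque-positive dentures, every value halves.

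**Dentures needed for a 10-point drop at N = 43.** k = 0.10 × 43/p:

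- p = 20%: 21.5, so 22 dentures (11 patients)
- p = 50%: 8.6, so 9 dentures (5 patients)
- p = 80%: 5.4, so 6 dentures (3 patients)

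**Comparison with sampling error.** At p = 50% and n = 43, the 95% half-width is 1.96 × √(0.25/43) = 14.9 points, ignoring clustering of dentures within patients. With one or two carried-in patients, the worst-case drop at N = 43 (2.3 or 4.7 points) is well inside that.

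**Would a different order help?** A carried-in denture may have been cleaned, stored or handled before handover. A score taken on receipt would therefore not be comparable with one from an attending patient. Leaving these dentures out of the plaque summary would reduce n from 43 to 41, 39 or 35 (1, 2 or 4 patients) and widen the half-width from 14.9 to 15.3, 15.7 or 16.6 points. No option gives a clean plaque measurement in this subgroup.

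**The case for a change.** The strongest case for a change is that the sponsor created this subgroup and then described no procedure for it. If the sequence presupposes a patient who is present, carried-in dentures have no stated procedure at all, and handling could differ from one denture to the next. The gap also reaches beyond plaque, since the mucosa, oral health and natural-tooth items cannot be scored without the patient and the text does not say how to record them. A sentence and a flag on the case report form would cost almost nothing.

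The silence is real, and so is the direction of any error. That does not make the design faulty. The patient-dependent items will be missing whatever is written, and an examiner can only leave them blank. An examiner who must report plaque has no reason to clean it off first and then score it. The text at hand also stops at section 4, and a synopsis would not normally set out the scoring order item by item, so its silence is weak evidence about how the examination is done.

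**Conclusion.** The concern does not call for a change. It depends on applying to carried-in dentures an order that the plan describes for attending patients, and on plaque then being scored on a freshly cleaned surface. What remains is an unwritten handling detail for a subgroup that may be empty, and dental examiners can be expected to fill it sensibly.

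Under the worst-case assumption that cleaning hides all plaque, one or two carried-in patients would move recorded prevalence by 2.3 or 4.7 points (50% prevalence, 43 dentures). Larger shifts need several such patients, high prevalence or a smaller denominator. These sizes rest on assumed counts, prevalence and misclassification, because the documents give none of them. The plaque score of attending patients is not in question, and denture survival is unaffected. The analysis is largely descriptive, has no control group, and no test or decision resting on plaque is described.
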